9. STATISTICAL METHODS AND DETERMINATION OF SAMPLE SIZE

9.1 Sample Size Determination

The researchers could not find an evidence-based measure of effect size from the existing literature. Therefore, this project will be considered a pilot study. The researchers believe there will at least be 10-20% reduction in complications associated with the treatment based on clinical experience. An *a priori* sample size calculation was performed using a 20% reduction, and with a two-tailed hypothesis, a power of 80%, and an equal allocation ratio to treatment arms, a total of $n = 100$ participants was generated. Therefore, the researchers plan on enrolling $n = 50$ participants in each treatment arm, totaling $n = 100$ participants. The effect size yielded from the final analysis will be used to power a future, larger trial between the two treatment arms.

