differences at baseline will be accounted for in the primary analysis using logistic regression. Chi-square or Fisher's Exact test will be performed to compare the treatment arms on distinguishing extravasation post-closure at the end of the procedure (yes/no), comparing the need for open vascular surgery (yes/no), utilizing a PTA/stent to help with hemostasis or local vascular complications (yes/no), bleeding/hematomas (yes/no), pain or numbness in the distal extremity (yes/no), mortality related to complications associated with the vascular closure site (yes/no), and conversion to general anesthesia due to additional procedures required to address CFA access site complications (yes/no). Cross-tabulation tables with frequencies, percentages, and associated OR with 95% CI will be reported and interpreted for all bivariate analyses of categorical, secondary outcomes. For count variables and non-normal continuous parameters (number of perclose devices, LOS, and serum creatinine), Mann-Whitney U tests will be performed to compare the two treatment arms. Medians and interquartile ranges will be reported and interpreted for the non-parametric analyses of the count and continuous parameters. Survival analysis will be performed using Kaplan-Meier in order to compare the two treatment arms on "time-to-event" outcomes. Mean and median times to events will be presented. Log-rank, Breslow, and Tarone-Ware tests will be used to compare the respective groups. Survival plots will also be graphed. All analyses will be performed using SPSS Version 29 (Armonk, NY: IBM Corp.) and statistical significance will be assumed at an alpha value of 0.05.

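### Ten secondary outcomes and three rank tests on unnamed time-to-event outcomes share one 0.05 rule, with no main test and no exploratory label (minor)

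*Combined protocol and SAP*

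**What the plan says.** All of this is in Section 9.2 (Statistical Methods) unless stated.

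- **Seven binary secondary outcomes.** The list opens with "Chi-square or Fisher's Exact test will be performed to compare the treatment arms on distinguishing extravasation post-closure at the end of the procedure (yes/no" and continues with open vascular surgery, PTA or stent, bleeding or haematoma, distal pain or numbness, closure-site mortality, and conversion to general anaesthesia. Odds ratios with 95% CI are planned for these.
- **Three count or continuous outcomes**, given as "number of perclose devices, LOS, and serum creatinine), Mann-Whitney U tests will be performed to compare the two treatment arms". Medians and interquartile ranges are planned, with no interval for the difference between arms.
- **Time-to-event outcomes.** "Survival analysis will be performed using Kaplan-Meier in order to compare the two treatment arms on" outcomes of this type, none of which is identified. For these, "Log-rank, Breslow, and Tarone-Ware tests will be used to compare the respective groups".
- **Threshold.** The section closes with "statistical significance will be assumed at an alpha value of 0.05". There is no multiplicity adjustment, testing order or exploratory label.

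Section 9.1 calls the project a pilot, specifies a calculation "with a two-tailed hypothesis, a power of 80%, and an equal allocation ratio to treatment arms", and states that "the researchers plan on enrolling $n = 50$ participants in each treatment arm".

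**The concern.** Two separate gaps meet in one section.

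First, ten secondary comparisons are each judged at 0.05, and nothing says that a result below that line is only descriptive. If IVL has no effect, one or more of the ten may still be written up as a significant difference between arms.

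Second, the survival analysis has no stated target. No objective in Section 3.2 and no endpoint in Section 7 is expressed as a time to an event. Mortality is analysed as yes/no and length of stay by Mann-Whitney. Both the choice of outcome for a Kaplan-Meier comparison and the choice among three differently weighted tests could therefore be made after the data are seen.

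At stake is how far a reader can trust any secondary result called significant. The primary comparison of access site complications is not affected by this.

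**Working it through.** The plan states no family-wise error rate, so there is no figure of its own to reproduce.

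**Inputs from the documents:** 0.05 per test; two-sided (stated in Section 9.1 for the sample size); 50 per arm; seven binary and three Mann-Whitney outcomes. **Assumed, because the documents are silent:** event rates and the correlation between outcomes.

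**1. Ceiling, ten independent tests of full size.**
- Either direction: 1 − 0.95^10 = 40.1%.
- In IVL's favour only, at 0.025 per test: 1 − 0.975^10 = 22.4%.

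**2. Why the real figure is lower.** With rare events, Fisher's exact test seldom rejects. Taking chi-square, or Fisher when the smallest expected count is below 5, the exact size at 50 per arm is:

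| Event rate | Size |
|---|---|
| 2% | 0.0004 |
| 5% | 0.0088 |
| 10% | 0.0406 |
| 15% | 0.0540 |
| 20% | 0.0521 |

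**3. Middle rates, independent outcomes.** Assume 15, 5, 10, 20, 15, 2 and 5% for the seven binary outcomes in the order listed above, and full size for the three Mann-Whitney tests.
- Either direction: 1 − (0.946² × 0.9912² × 0.9594 × 0.9479 × 0.9996 × 0.95³) = 1 − 0.685 = 31.5%.
- In IVL's favour, halving each size: 1 − (0.973² × 0.9956² × 0.9797 × 0.97395 × 0.9998 × 0.975³) = 1 − 0.830 = 17.0%.

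**4. Simulation under the null, ten outcomes, 50 per arm, either direction.** Correlation is that of the underlying latent variables.

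| Assumed binary rates (%) | Correlation | Any p<0.05 |
|---|---|---|
| 5, 2, 3, 10, 5, 0.5, 1 (low) | 0 / 0.3 / 0.6 | 18.9 / 19.6 / 18.4% |
| 15, 5, 10, 20, 10, 1, 3 (middle) | 0 / 0.3 / 0.6 | 30.4 / 28.2 / 25.9% |
| 15, 5, 10, 20, 15, 2, 5 (middle) | 0 / 0.3 / 0.5 | 31.9 / 29.3 / 28.5% |
| 30, 20, 25, 30, 30, 5, 15 (high) | 0 / 0.3 / 0.6 | 37.2 / 34.7 / 30.0% |

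A further low set (1-8%) gave 17-18%. The low end is driven by the three Mann-Whitney outcomes, which alone give 1 − 0.95³ = 14.3% if independent.

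**5. Simulation, in IVL's favour only.** About 9-10% at low rates and 14-16% at middle rates. A separate middle-rate run, with its own assumed distributions for the Mann-Whitney outcomes, gave 15-18%, in line with the 17.0% in step 3. High rates were not simulated in one direction; the 22.4% ceiling bounds the independent case.

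**6. Best of three rank tests on one outcome.** If independent, three tests would give 14.3%. They share the same data and are highly correlated, so the simulated results are much lower:
- 10%, 20% or 50% of patients with the event: 5.1%, 4.7%, 6.3%.
- All patients with the event (for example time to discharge): 6.9% in one simulation and 7.8% in another, against about 5% for a single test, so roughly 2-3 points more.
- 15% of patients with the event, all in days 0-3: 4.7%, no inflation. Section 3.3 expects events within 3 days.

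Per-protocol repeats and any further time-to-event outcomes are left out; they could only raise the figures.

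**The case against.** The case for leaving the text alone has substance. The trial is a pilot. One primary outcome is named and the rest are listed as secondary. Odds ratios with 95% CI are already required for seven of the ten outcomes. The closing sentence on 0.05 can be read as a conventional threshold attached to a statement about software. Choosing among three rank tests costs very little error.

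Most of this stands, and it is why the point is minor. It does not close the gap. Section 9.2 gives no other threshold and no exploratory label, so a reader following the text would call any secondary p<0.05 significant. The time-to-event outcomes are undefined whatever the error rate.

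Three stronger readings are tempting, and the documents do not support them:

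- **A reader might infer that about three null trials in ten would show a false IVL benefit.** That size of figure counts differences in either direction and holds only at middle assumed event rates. For a false benefit it is about half, and the documents give no event rates to fix it.
- **A reader might infer that three rank tests multiply the error threefold.** Step 6 shows that they do not.
- **A reader might infer that a chance secondary finding will size the next trial.** Section 9.1 carries forward the effect size from the final analysis, and its calculation concerns the reduction in complications. Nothing there says that a secondary outcome will be selected.

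**Conclusion.** The point holds as a minor one. Ten secondary outcomes and an unspecified number of survival comparisons fall under a 0.05 rule, with no main rank test and no exploratory label.

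With no true effect, at least one secondary p<0.05 in either direction has a probability of roughly 17-40%, the upper end being the independent-test ceiling. In IVL's favour alone it is about half, roughly 9-16% in simulation at low to middle rates, with a ceiling of 22%. These ranges depend on assumed event rates and correlations.

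The three rank tests matter because the choice is left open, far more than through error inflation. The unnamed outcomes are the larger gap in the survival analysis and need no simulation to establish. Severity stays low because the trial is a pilot and the primary analysis is unaffected.

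**What to change.** Amend Section 9.2 as follows.

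1. Name each time-to-event outcome, with its origin, event and censoring rule, or delete the survival text.
2. If it is kept, designate the log-rank test as the single test. Drop Breslow and Tarone-Ware, or show them only as sensitivity analyses.
3. State that 0.05 applies to one designated primary comparison of access site complications. The section plans both an unadjusted and an adjusted analysis, so say which one carries it.
4. State that secondary outcomes are exploratory, reported as estimates with 95% CI and not declared significant. For the three Mann-Whitney outcomes, add an interval for the difference, for example Hodges-Lehmann.

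The cost is a few sentences, with no extra patients or data. The downside is that no significance claims can be made from secondary outcomes.

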10. STUDY MANAGEMENT

The PI and study team have the site resources, time availability, and the patient population needed to complete this protocol under GCP guidelines. The PI is ultimately responsible for the conduct of the trial; however, he will delegate authority to appropriate members of the research team. The PI will ensure the following:

- Study team complies with GCP and other regulatory requirements.
- The study team allows monitoring and auditing of regulating institutions.
- Ensures person delegated trial responsibilities are qualified and trained appropriately.
- Ensure that study team members have sufficient time to properly conduct and complete the trial.
- Ensure that all persons assisting with the trial are adequately informed about the protocol, the treatments being administered, and their study-related duties and functions.
- Ensures compliance with GCP guidelines regulatory requirements.
- Will maintain a list of research team members and delegated duties.
- Assures protocol compliance.
- Reports protocol non-compliance appropriately.
- Obtains IRB approval.
- Following regulations and guidelines to protect subject rights, safety, and welfare.
- Assures compliance by all research team members of GCP regulations

11. DATA MANAGEMENT

Data will be collected and managed by trained study team members. Data will be stored in the Office of Research Support (ORS) by the study team, which has limited access. Data collected

during the study will be retained in patients' research records for at least 6 years after the study is completed. At that time, the research information not already in the patients' medical records will be destroyed, per institutional guidelines.

11.1 Data Protection

Throughout the study, measures to ensure the privacy of information on study subjects will be maintained. All project investigators and staff have been trained in the use of human subjects in research and have received training in the new HIPAA regulations. Subjects and staff will be informed of the confidentiality of information and assured that data will be used only for statistical purposes in which the individual cannot be identified. Conversely, no identifiable information on any individual will be released to anyone other than project personnel without a signed medical release from the subject, or where appropriate, the next of kin or a physician in case of a life-threatening emergency to the subject. All project personnel will be instructed not to discuss any cases with persons other than project personnel.

For this specific project, it may be required to collect PHI such as age, DOB, Medical Record Number and dates of diagnoses. Only the study team will have access to this data, and it will not be shared with anyone outside of the study team. Data will be collected on paper source documents and transcribed into the GSM REDCap system. Only study team members will have access to the database. The database will utilize the study number assigned and will not include the subject's name or MRN. All subjects will have an assigned number. All completed paper forms will be kept in locked files in locked rooms to which only project personnel have access.

11.2 Data and Safety Monitoring

Monitoring will be completed by the GSM Office of Research Support and/or The Office of Clinical Trials and include a review of original case records. It will include monitoring to assess patient safety, the consent process, record-keeping, protocol adherence, and data collection. The Investigator will record all protocol deviations. Unexpected clinically significant adverse events will be reported to the IRB. In general, the investigators will monitor any adverse reaction to study procedures conducted during the study. Any missing data will be omitted from the final statistical analysis.

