3.2.2 Secondary Objectives

1. Determine the clinical outcomes between groups.
2. Distinguish extravasation post closure at the end of the procedure.
3. Compare the need for open vascular surgery between groups.

4. Examine PTA or Stents to the CFA to help hemostasis or local vascular complications between groups.
5. Number of Perclose devices used between groups.
6. Compare Bleeding/Hematoma between groups.
7. Examine the difference in hospital length of stay between groups.
8. Examine renal function post procedure
9. Difference in pain or numbness in the distal extremity between groups
10. Mortality related to complications from vascular closure site between groups.
11. Conversion to general anesthesia due to additional procedures required to address the CFA access site complications between groups.

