3.3 Study Duration

We plan to enroll up to a total of 100 patients, 50 patients in each group. The total study duration will be approximately 12 months post IRB approval and study initiation. We will follow patients for 3 months post procedure for any adverse events; however, we would expect to see them within 3 days if there are events to occur.

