3.5 Discontinuation of Subjects

An individual patient is to be withdrawn from the trial if any of the following criteria apply:

- The patient withdraws consent, without the need to justify the decision
- The patient is no longer able to participate for medical reasons (e.g., surgery, AEs, or other diseases)
- Decision by the PI to discontinue a specific patient for his/her safety (e.g., in case of SAEs)

Data of patients who discontinue or withdraw prior to enrollment will be entered in the study database and will be listed. Data of patients who discontinue or withdraw after enrollment will be documented and the reason for withdrawal will be recorded in the study record. The data will be included in the study database and will be reported.

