4. STUDY PROCEDURES

4.1 Screening and Enrollment

Screening assessments will be completed by the study team on a day before the procedure to allow patients time to review and ask questions. Assessments will be initiated after the Informed Consent Form (ICF) Process. A study designee will present the study information to the patient. They will explain the purpose, risk, and benefits to the subject and present them with an IRB approved ICF. The potential participant will be given ample time to read the ICF and all questions and concerns from the subject will be addressed by a study team member. No procedures will be initiated prior to the subject signing and dating the ICF. After the subject signs the ICF, a copy will be given to them for their records. Participants will be informed that they can decline participation in the study without any effect on their health care. They can also withdraw their consent, including the consent to do various screening tests, at any time.

4.2 Datapoints/procedures to be collected/obtained:

- Informed Consent
- Medical History Review for Inclusion/Exclusion Criteria
- Concurrent Medication Review
- Pre-TAVR CT scan review
- Review of pre procedure laboratory results
- Demographics
- Pre-procedure consultation/progress notes
- Post procedure notes (consult, progress, discharge summary)
- Post procedure laboratory results and imaging
- Post discharge follow up office notes and vital signs

If subjects meet all I/E criteria, they will be Enrolled, and the following will be recorded

- Flow rates prior to and post procedures
- Documentation of extravasation post closure at the end of the procedure.
- If open vascular surgery occurred
- Number of perclose devices used

- Bleeding/Hematoma outcomes
- Hospital length of stay
- Renal function lab results post procedure
- Pain or numbness in the distal extremity post procedure
- Whether conversion to General Anesthesia was needed during procedure
- Review of post-procedure laboratory results
- Surgical/procedure reports
- Mortality
- Discharge summary
- Adverse event monitoring

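### Patients can be withdrawn for reasons that overlap the outcomes, no passage provides for collecting events that first arise afterwards, and 11.2 omits missing data

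*Combined protocol and SAP*

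**What the plan says.** Besides withdrawal of consent, section 3.5 gives two grounds on which a patient leaves the trial: "The patient is no longer able to participate for medical reasons (e.g., surgery, AEs, or other diseases"; and "Decision by the PI to discontinue a specific patient for his/her safety (e.g., in case of SAEs". For those who leave after enrollment, the reason is recorded and "The data will be included in the study database and will be reported".

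Section 3.3 sets the size and the follow-up: "We plan to enroll up to a total of 100 patients, 50 patients in each group", and "We will follow patients for 3 months post procedure for any adverse events". It adds that events are expected within 3 days. Section 3.2.2 includes the outcome "Mortality related to complications from vascular closure site between groups", and section 7.2 counts related AEs and SAEs. Section 4.2 lists "Post discharge follow up office notes and vital signs" among the records to be reviewed.

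Section 8 records AEs judged at least possibly related to the study procedure. Each is evaluated from its onset until it resolves or the patient is stable. The AE outcome categories include death, and one for an AE still ongoing when the patient leaves the study. Withdrawal because of an AE is one of the listed actions.

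Section 9.2 makes all inferential analyses intention-to-treat. Section 11.2 says: "Any missing data will be omitted from the final statistical analysis". Neither section describes a sensitivity analysis for missing outcomes.

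**The concern.** Two of the three grounds for withdrawal are illustrated by events that the trial also measures. Open vascular surgery is a secondary outcome, and related AEs and SAEs are the safety endpoints. If follow-up ends at withdrawal, the patients whose later status is unknown could be mainly those who had a complication. Omitting them would leave a 3-month safety summary that rests on a selected part of the randomized sample, although the plan describes its inferential analyses as intention-to-treat.

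At stake is whether the 3 months of follow-up cover everyone who was randomized. In a trial of 50 per arm with few late events expected, a handful of patients of unknown status can matter for these outcomes.

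**Working it through.** **1. Is collection after withdrawal provided for?** The passages that might provide it are these:

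- 3.5 keeps and reports the data of withdrawn patients. Keeping data is not the same as continuing to collect it.
- 3.3 promises 3 months of follow-up for patients in general. It does not say whether this continues for a patient withdrawn under 3.5.
- 4.3.2 asks patients to try to complete the study. It does not address those whom the protocol or the PI withdraws.
- Section 8 follows an AE from its onset. It does not cover a new event in a patient who has left, and its ongoing category lets an unresolved AE be closed when participation ends.

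None of them says that outcomes first arising after withdrawal are collected.

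**2. Which outcomes are exposed?**

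- Procedural and in-hospital outcomes are mostly known before withdrawal could matter, and 3.5 retains them. This covers the access-site outcomes as the protocol expects them to occur.
- Related AEs and SAEs (7.2) are exposed if they begin after withdrawal and within 3 months. Unrelated events are outside the count in any case.
- Closure-site death is exposed if the complication behind it begins after withdrawal, or if an earlier AE had already been closed as stable or ongoing. A death from an AE still under evaluation is largely covered by section 8.
- In any Kaplan-Meier analysis (9.2 names no outcome and no censoring rule), withdrawn patients would ordinarily be censored rather than dropped. Censoring prompted by surgery or an SAE may be informative.

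**3. What bound can be computed?** The plan gives no withdrawal or late-event rate, so it has no figure of its own to reproduce here. The only documented input is 50 per arm (3.3 and 9.1). Let x be observed late events and m patients of unknown status, in the IVL (I) and control (C) arms.

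- Omission: xI/(50 − mI) − xC/(50 − mC)
- Best case for IVL: xI/50 − (xC + mC)/50
- Worst case for IVL: (xI + mI)/50 − xC/50
- Width of the range: (mI + mC)/50, which is 2 percentage points per unknown patient whatever the event counts

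So 1, 2, 4 or 10 unknown patients in total give widths of 2, 4, 8 or 20 points.

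**4. Illustration.** All counts here are assumed: 2 IVL and 5 control late events observed, and 4 patients unknown.

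- 1 IVL and 3 control unknown: omission gives 2/49 (4.1%) against 5/47 (10.6%), a difference of −6.6 points. Best case is 2/50 − 8/50 = −12; worst case is 3/50 − 5/50 = −4.
- 3 IVL and 1 control unknown: omission gives 2/47 (4.3%) against 5/49 (10.2%), a difference of −5.9 points. Best case is 2/50 − 6/50 = −8; worst case is 5/50 − 5/50 = 0.

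The omission results are close to each other, but the ranges they conceal differ. With no unknown patients there is no effect.

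**The case against.** The strongest reply is that little is left to lose.

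- **The grounds are conditional.** Surgery counts only if the patient can no longer take part, and the SAE ground is a PI decision. The intervention is a single procedure and later data come from office notes, so such withdrawals may be rare. This stands: the documents do not show that they are likely.
- **Data already collected are kept, and open AEs are followed.** This also stands, and it is why the exposure is confined to new events and to AEs already closed.
- **No between-arm test of AEs or SAEs is specified.** True. Section 7.2 lists counts, and closure-site mortality is the only exposed outcome with a named test; it has no stated time window. The tension with intention-to-treat therefore touches little of the inferential plan. Analysing by assigned arm while omitting missing values is weak practice rather than a flat contradiction.
- **The bound is generic.** Two points per patient holds for any trial with 50 per arm, the examples use assumed counts, and 9.2 reports odds ratios rather than risk differences. All true. The bound shows sensitivity and is not evidence of bias in this trial.
- **The consent form is not among the pages reviewed.** It may contain terms on data use after withdrawal, so it should be checked.

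What remains is a stated omission rule and no stated collection after an outcome-related withdrawal, in a protocol that chose to follow patients for 3 months.

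**Conclusion.** The point holds in a limited form, and the wording should be changed. It concerns new procedure-related AEs and SAEs, and closure-site deaths from complications that begin after withdrawal or after an earlier AE was closed, up to 3 months. It extends to informative censoring in any Kaplan-Meier analysis of such events. The only supportable size is 2 percentage points of added uncertainty in the risk difference per randomized patient of unknown status.

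A reader might infer more, and the documents do not support it:

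- That the primary comparison is biased. Events are expected within 3 days and data gathered before withdrawal are retained.
- That every patient with open surgery or an SAE is withdrawn and the event discarded. The grounds are conditional or discretionary, and 3.5 keeps what was collected.
- That omission favors IVL, or either arm. No rates are given, so direction cannot be derived.
- That creatinine and limb pain or numbness are equally at risk. They are listed only as post-procedure, with nothing to show that they would be assessed after withdrawal.

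The conclusion assumes that follow-up stops at withdrawal because nothing says that it continues. If the consent form or site practice already provides for it, only the missing-data wording needs attention.

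**What to change.** In 3.5, separate ending study participation from withdrawing consent to data collection. State that outcomes and related AEs are collected to 3 months, from the records already reviewed under 4.2, for every randomized patient unless consent to data collection is withdrawn. Clinical decisions do not change.

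Replace the missing-data sentence in 11.2 with four statements:

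1. All randomized patients are analysed as assigned.
2. Events observed before withdrawal count.
3. Missing outcomes are reported by arm, with the reasons recorded under 3.5.
4. A best-case/worst-case sensitivity analysis is given for binary outcomes with missing data.

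The cost is the protocol wording, a few extra chart reviews, and a check that the consent form covers record-based follow-up after withdrawal. The sample size does not change.

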9.2 Statistical Methods

Descriptive and frequency statistics will be used to describe the demographic, clinical, and prognostic characteristics of the randomized sample. All inferential analyses will be performed in an "intention-to-treat" fashion. A "per-protocol" analysis will also be performed. For the primary outcome, access site complications, both bivariate (chi-square or Fisher's Exact test) and multivariate (logistic regression) analyses will be performed to compare the two groups. Unadjusted odds ratios (OR) with 95% confidence intervals (95% CI) will be generated for the chi-square analyses and adjusted odds ratios (AOR) with 95% CI will be calculated for the logistic regression analyses. Baseline demographic, clinical, and prognostic characteristics will be compared between the treatment arms using between-subjects inferential analyses after randomization to test for any significant differences. Any significant

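### The rule to omit missing data has no exception for baseline covariates, so patients with known arm and outcome can drop out of the adjusted primary analysis; the expected loss is modest and cheap to avoid

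*Combined protocol and SAP*

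**What the plan says.** Section 11.2 (Data and Safety Monitoring) contains the only missing-data rule: "Any missing data will be omitted from the final statistical analysis". It does not separate outcomes from covariates, and it does not say whether omission is per analysis or per patient. No other section provides for imputation, a missing category or a sensitivity analysis.

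On access site complications, which are the primary outcome, section 9.2 (Statistical Methods) plans that "both bivariate (chi-square or Fisher's Exact test) and multivariate (logistic regression) analyses will be performed to compare the two groups". It reports an unadjusted odds ratio (OR) from the first of these, and for the second "adjusted odds ratios (AOR) with 95% CI will be calculated for the logistic regression analyses". The covariates are not named in advance. The arms are compared at baseline after randomization, and any significant "differences at baseline will be accounted for in the primary analysis using logistic regression". The threshold is general: "statistical significance will be assumed at an alpha value of 0.05". The same section promises: "All inferential analyses will be performed in an 'intention-to-treat' fashion".

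Section 4.2 lists the sources of the baseline data, among them history, medications, CT, demographics, notes and "Review of pre procedure laboratory results". Section 9.1 arrives at 100 patients "using a 20% reduction, and with a two-tailed hypothesis, a power of 80%, and an equal allocation ratio to treatment arms". It states no control-arm complication rate and no allowance for missing data.

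**The concern.** A logistic regression cannot use a patient who lacks one of its predictors. Under section 11.2 as written, a gap in a selected baseline variable therefore removes the whole patient from the adjusted primary analysis, although everything needed for the randomized comparison (arm and outcome) was observed. This is a different problem from outcomes lost after withdrawal, where keeping the patient requires an assumption about data nobody saw.

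Three things are at stake: precision, in a 100-patient trial with few events; the intention-to-treat promise in section 9.2; and the comparison of the OR with the adjusted odds ratio (AOR), which is harder to read if the two come from different patients. The number lost cannot be known in advance, because the covariates are chosen after randomization. Section 9.1 also plans to power a larger trial from the effect size found here, and the AOR is one candidate for it.

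**Working it through.** **1. The plan's own figure.** The control rate is not stated, so it has to be assumed. With the pooled two-proportion formula, n per arm = [1.96·√(2p̄(1−p̄)) + 0.84·√(p₁(1−p₁)+p₂(1−p₂))]² / (p₁−p₂)². For 25% vs 5%, p̄ = 0.15, and n = [1.96·√0.255 + 0.84·√0.235]² / 0.04, which rounds up to 49 per arm, or 98 in total. That is close to the stated 100. Other control rates with a 20-point difference give about 70 (20% vs 0%) to 194 (60% vs 40%). The pair 25% vs 5% is used below as the one closest to the plan, and 30% vs 10% as an alternative.

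**2. What losing patients costs.** With the same formula at 50·(1−m) patients per arm, where m is the share of patients missing a selected covariate:

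| m | Patients left | Power, 25% vs 5% | Power, 30% vs 10% |
|---|---|---|---|
| 0 | 100 | 80.9% | 71.1% |
| 5% | 95 | 78.9% | 68.9% |
| 10% | 90 | 76.6% | 66.5% |
| 20% | 80 | 71.5% | 61.2% |

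This is an unadjusted approximation. It shows only the effect of patient numbers.

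**3. How many covariates enter.** Under valid randomization, a variable tested at 0.05 is selected about 5% of the time. For independent candidates, the chance that none is selected is 0.95¹⁰ = 60% with 10 and 0.95²⁰ = 36% with 20. Three or more are selected in 1.2% and 7.5% of trials, and four or more in 0.1% and 1.6%. The plan does not give the number of candidates; 10 and 20 are assumptions.

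**4. Expected patients dropped.** Ignoring overlap, this is candidates × 0.05 × patients missing each one. The low end is 10 × 0.05 × 2 = 1 and the high end is 20 × 0.05 × 5 = 5, out of 100.

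**5. Simulation under the plan's selection rule.** There were 2,000 trials per scenario with 50 patients per arm. Covariates were selected by t-test at 0.05, four candidates were prognostic (log-odds 0.5), and values were missing completely at random. Each cell gives power under omission vs pooled-mean fill:

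| Risks | Candidates | 2% missing | 5% missing |
|---|---|---|---|
| 25% vs 5% | 10 | 73.0 vs 73.6% | 71.1 vs 73.2% |
| 25% vs 5% | 20 | 69.2 vs 70.8% | 68.6 vs 72.8% |
| 30% vs 10% | 10 | 69.6 vs 69.8% | 66.1 vs 67.6% |
| 30% vs 10% | 20 | 69.0 vs 70.2% | 65.8 vs 68.4% |

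The differences run from 0.2 to 4.2 points. Mean patients dropped are 1 to 5, matching step 4. The p<0.05 verdict differs in 1.6% to 5.9% of trials. A repeat over the same assumed ranges gave about 1 to 4 points and changed verdicts in about 2% to 7% of trials, with no covariate entered in about 33% to 62% of them.

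**6. Whether filling is safe.** With no true effect (15% in both arms, three continuous covariates in the model, 5% missing each), pooled-mean fill rejected in 4.2% of 6,000 simulated trials. Type I error was not inflated. Filling of categorical covariates was not simulated.

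**The case against.** The strongest reply is that the rule will seldom bite. A covariate must first be selected by a baseline significance test and must then be missing for someone. The trial is prospective and single-center, the calcium arc on CT is an inclusion criterion, the baseline items are listed study datapoints, and section 11.2 provides for monitoring against original records. The documents give no missingness rate, and 5% missing independently on every variable may be pessimistic. All of this stands, and it is why the expected loss is small.

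A reader might infer something stronger: that section 9.2 puts a full set of baseline variables into the model. If four covariates were always entered, each 5% missing, about 18 of 100 patients would drop and power at 25% vs 5% would be 61% under omission vs 76% with mean fill. The documents do not support this, because only significantly different variables enter and four or more would be rare (step 3).

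A reader might also take it as settled that the OR keeps everyone while the AOR uses a subset. Section 11.2 does not say so. If omission is per patient, the two share one set, but the unadjusted test then loses patients as well. Nor would a gap between OR and AOR by itself show an effect of omission, since odds ratios are non-collapsible and the two can differ on identical patients. Finally, section 9.1 does not say that the AOR, rather than the OR, will power the next trial.

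None of this defends the rule itself. It discards patients whose arm and outcome are known and gains nothing in return.

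**Conclusion.** The point holds at modest size. The figures of about 1 to 5 patients dropped, 1 to 4 points of power lost and a changed verdict in 2% to 7% of trials apply to omission per analysis. They rest on assumed risks of 25% vs 5% or 30% vs 10%, 10 to 20 independent candidate variables, and 2% to 5% missing completely at random. Fewer gaps, or gaps concentrated in the same patients, would make the loss smaller. Removing every patient with any missing item from all analyses would make it larger; that case is not sized here. Because the text leaves the scope of omission open, it needs clarifying whichever reading was meant. The change is worth making because the rule conflicts with section 9.2's own analysis set and the remedy costs almost nothing, not because a large loss is expected.

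**What to change.** In sections 11.2 and 9.2, state that the omission rule does not apply to baseline covariates. Suggested wording:

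*In the adjusted primary analysis, a missing baseline covariate is replaced by a single pooled value computed without regard to arm or outcome: the mean for a continuous variable, the most frequent category for a categorical one. A separate missing category is used only if enough patients fall in it to avoid separation. Every randomized patient with a primary outcome is included in both the OR and the AOR, and the number analysed is reported for each. The complete-case AOR is reported as a sensitivity result.*

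The condition on the missing category matters. At 25% vs 5% or 30% vs 10%, about 15 to 20 events are expected in all (50 × 0.25 + 50 × 0.05 = 15; 50 × 0.30 + 50 × 0.10 = 20), so a category holding a handful of patients could be nearly empty of events.

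The cost is a few sentences and a few lines of SPSS syntax, with no new data, patients or visits. The downside is a slightly weaker adjustment for the few patients with a filled value. Offsetting the loss by enrolment instead would take 106 patients at 5% loss (100/0.95) or 112 at 10% (100/0.90).
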